11.3 Vital Signs

Vital signs are collected over two days (Day 1 and Day 2) at each infusion at following timepoints:

- Day 1/2-15 mins before start of IV infusion
- Day 1/2-30 mins after start of IV infusion
- Day 1/2- 60 mins after start of IV infusion
- Day 1/2-30 mins after completion of IV infusion

The vital signs parameters were recorded heart rate, respiration rate, systolic and diastolic blood pressure and temperature, with timepoint and indication of abnormal or not.

The changes of vital signs from pre-infusion (15 mins before start of IV infusion) to each of the post infusion timepoints will be summarized for each day at each visit.

All vital signs data will be listed.

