4.4.2 Dosage and dosage regimen of the investigational products

4.4.2.1 Dosage of investigational product (test): Flebogamma® 5% DIF

Dosage and regimen:	2 g/kg body weight administered over 2 consecutive days (1 g/kg infused on Day 1 and 1 g/kg infused on Day 2).
	1 g/kg body weight administered on 1 day (Day 1 or Day 2) (if randomized to IVIG 1 g/kg arm)

Administration via: Intravenously.

Administration form: Investigational product will be prepared and administered per Pharmacy Manual.

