4.4.2.3 Dosage regimen of investigational product (test and placebo)

At Stage 1, Flebogamma[®] 5% DIF at a dosage of 2 g/kg body weight (IVIG 2 g/kg arm), Flebogamma[®] 5% DIF at a dosage of 1 g/kg body weight (IVIG 1g/kg arm), and Normal Saline Solution (placebo) will be administered every 4 weeks, with each dose being

administered over a dosing period of 2 consecutive days (Day 1 and Day 2) up to 13 infusions visits, that is, 26 intravenous infusions.

For the purpose of maintaining the treatment blind, the volume of each administration of investigational product in the IVIG 1 g/kg and placebo arms will be equivalent to that for the IVIG 2 g/kg arm so that all subjects receive the same total dose volume for all treatment arms. The total volume for each dose of investigational product will be administered over 2 consecutive days as follows:

- IVIG 2 g/kg arm A total dose of 2 g/kg of body weight of Flebogamma® 5% DIF will be administered over 2 consecutive days.
- IVIG 1 g/kg arm A total dose of 1 g/kg of body weight of Flebogamma[®] 5% DIF will be administered on 1 day, and a total dose of 20 mL/kg of body weight Normal Saline Solution (equivalent volume of 1 g/kg of body weight Flebogamma® 5% DIF infusions) will be administered on a separate day, for a total dosing period of 2 consecutive days. The order of 1 g/kg of body weight of Flebogamma® 5% DIF or 20 mL/kg of body weight Normal Saline Solution infused on 2 consecutive days will be randomly determined for each subject by the IWRS, which will remain the same for the subject for all infusion visits during the treatment period.
- Placebo arm A total dose of 40 mL/kg of body weight Normal Saline Solution (equivalent volume of 2 g/kg of body weight Flebogamma® 5% DIF infusions) will be administered over 2 consecutive days.

Randomized Treatment Assignment	Day 1 (Day 1 Dose per IWRS Randomization list)	Day 2 (Day 2 Dose per IWRS Randomization list)
IVIG 2 g/kg	1g/kg Flebogamma® 5% DIF	1g/kg Flebogamma® 5% DIF
IVIG 1 g/kg	1g/kg Flebogamma [®] 5% DIF OR 20 mL/kg Normal Saline as determined by the IWRS (the opposite treatment as Day 2)	1g/kg Flebogamma [®] 5% DIF OR 20 mL/kg Normal Saline as determined by the IWRS (the opposite treatment as Day 1)
Placebo	20 mL/kg Normal Saline	20 mL/kg Normal Saline

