Flebogamma[®] 5% DIF administered at a dosage of 1 g/kg body weight (IVIG 1 g/kg arm) will be infused on 1 day with a maximum of Flebogamma[®] 5% DIF 1 g/kg/day (Table 3). To maintain the blind, a total dose of 20 mL/kg of body weight Normal Saline Solution (equivalent volume of 1 g/kg of body weight Flebogamma[®] 5% DIF infusions) will also be administered on a separate day (Table 4), for a total dosing period of 2 consecutive days. The order of 1 g/kg of body weight of Flebogamma[®] 5% DIF or 20 mL/kg of body weight

Normal Saline Solution infused on 2 consecutive days will be randomly determined for each subject by the IWRS, which will remain the same for the subject for all infusion visits during the treatment period.

Normal Saline Solution administered at a dosage of 40 mL/kg body weight (placebo arm) will be infused over 2 consecutive days with a maximum of 20 mL/kg of body weight/day (Table 5).

Summary of IVIG 2 g/kg arm's dose to be administered according to body Table 2. weight

	Flebogamma® 5% DI	F (2 g/kg body weight)	Maximum daily dose
Body weight	IVIG (g)	IVIG (mL)	(mL) of Flebogamma [®] 5% DIF (20 mL/kg body
40.1	00 -	1.600T	weight/day)
40 kg	80 g	1600 mL	800 mL
50 kg	100 g	2000 mL	1000 mL
60 kg	120 g	2400 mL	1200 mL
70 kg	140 g	2800 mL	1400 mL
80 kg	160 g	3200 mL	1600 mL
90 kg	180 g	3600 mL	1800 mL
100 kg	200 g	4000 mL	2000 mL
110 kg	220 g	4400 mL	2200 mL

Summary of IVIG 1 g/kg arm's dose of Flebogamma® 5% DIF to be administered according to body weight

	Flebogamma® 5% D	IF (1 g/kg body weight)	Maximum daily dose (mL) of Flebogamma®					
Body weight	IVIG (g)	IVIG (mL)	5% DIF (20 mL/kg body weight/day)					
40 kg	40 g	800 mL	800 mL					
50 kg	50 g	1000 mL	1000 mL					
60 kg	60 g	1200 mL	1200 mL					
70 kg	70 g	1400 mL	1400 mL					
80 kg	80 g	1600 mL	1600 mL					
90 kg	90 g	1800 mL	1800 mL					
100 kg	100 g	2000 mL	2000 mL					
110 kg	110 g	2200 mL	2200 mL					

Table 4. Summary of IVIG 1 g/kg arm's dose of normal saline solution to be administered according to body weight

Body weight	Normal Saline Solution (20 mL/kg body weight)	Maximum daily dose (mL) of Normal Saline Solution (20 mL/kg body weight/day)
40 kg	800 mL	800 mL
50 kg	1000 mL	1000 mL
60 kg	1200 mL	1200 mL
70 kg	1400 mL	1400 mL
80 kg	1600 mL	1600 mL
90 kg	1800 mL	1800 mL
100 kg	2000 mL	2000 mL
110 kg	2200 mL	2200 mL

Table 5. Summary of placebo dose to be administered according to body weight

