11 SAFETY ANALYSIS

Safety analyses are based on the Safety Population. All combined safety data from both Stage 1 and Stage 2 together will be summarized by treatment arm. Safety analyses will be performed according to the actual treatment received.

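### The by-day vital-sign table mixes Flebogamma and saline infusions in the 1 g/kg arm, so it does not show a per-infusion effect for that arm

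*SAP*

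**What the plan says.** SAP 11.3 takes readings on Day 1 and Day 2 of every infusion visit: 15 minutes before the start, 30 and 60 minutes after it, and 30 minutes after completion. Changes from the pre-infusion reading "to each of the post infusion timepoints will be summarized for each day at each visit". The grouping comes from SAP 11: "All combined safety data from both Stage 1 and Stage 2 together will be summarized by treatment arm". The same section adds: "Safety analyses will be performed according to the actual treatment received". Neither section splits the 1 g/kg arm by product infused or by infusion order.

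The protocol fixes what each arm receives on each day:

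- **2 g/kg arm** (Protocol 4.4.2.1): "2 g/kg body weight administered over 2 consecutive days (1 g/kg infused on Day 1 and 1 g/kg infused on Day 2").
- **1 g/kg arm** (Protocol 4.4.2.1): "1 g/kg body weight administered on 1 day (Day 1 or Day 2"). Saline at 20 mL/kg is given on the other day. Protocol 4.4.2.3 says the order "will be randomly determined for each subject by the IWRS, which will remain the same for the subject for all infusion visits".
- **Placebo arm** (Protocol 4.4.2.2): saline at 20 mL/kg on both days.

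Protocol 4.4.4.3 applies one infusion-rate schedule to test product and placebo. Vital signs during infusions are a named safety endpoint (Protocol 9.1), and Protocol 10.1.3 says they will be evaluated for each subject and each infusion.

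**The concern.** In the 2 g/kg and placebo arms a by-day cell contains one product. In the 1 g/kg arm it contains Flebogamma for some subjects and saline for the rest, and the other day's cell is the reverse. The mean in such a cell is neither the change during a Flebogamma infusion nor the change during a saline infusion.

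Two comparisons are affected if the table is read per infusion. The 1 g/kg contrast with placebo is diluted, and the 1 g/kg arm looks milder than the 2 g/kg arm even though the Flebogamma dose on a Flebogamma day is the same in both. The dilution would carry into Stage 2 if 1 g/kg were selected, because Protocol 4.4.2.3 keeps the same two-day administration there and SAP 11 pools the stages.

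**Working it through.** The documents give no figure for this point, so there is none to reproduce. Their own arithmetic is consistent: 1 g/kg at 50 g/L is 1/50 × 1000 = 20 mL/kg, and 13 visits × 2 days = 26 infusions. Of these 26, 26 are Flebogamma at 2 g/kg, 13 at 1 g/kg and none on placebo.

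**Inputs**

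- d: mean Flebogamma-minus-saline change per infusion. Not in the documents; kept as a symbol, with d = 5 (arbitrary units) for illustration.
- pi: share of the 1 g/kg arm given Flebogamma on Day 1. Not in the documents; 0.5 assumed, with 1/3 to 2/3 shown.
- Arm size: 42 in Stage 1 (SAP 5.3).

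**Contrast with placebo, no carry-over**

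| | Day 1 | Day 2 | Two-day mean |
|---|---|---|---|
| 2 g/kg | d | d | d |
| 1 g/kg, general | pi × d | (1 − pi) × d | 0.5d |
| 1 g/kg, pi = 1/2 | 0.50d | 0.50d | 0.5d |
| 1 g/kg, pi = 1/3 | 0.33d | 0.67d | 0.5d |
| 1 g/kg, pi = 2/3 | 0.67d | 0.33d | 0.5d |

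The two-day mean does not depend on pi, because each subject has exactly one Flebogamma day: [pi × d + (1 − pi) × d]/2 = 0.5d.

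If the order were assigned by simple 1:1 randomisation in 42 subjects, the realised pi would lie in 0.5 ± 1.96 × √(0.25/42), or about 0.35 to 0.65, with 95% probability.

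A simulation with 42 subjects, pi = 0.5, d = 5 and an assumed SD of 10 (20,000 runs) gave 2.52 on Day 1 and 2.51 on Day 2 in the 1 g/kg arm, against 5 on each day at 2 g/kg. Splitting the same data by product gave 5.01 on Flebogamma days and 0.02 on saline days.

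**Carry-over**

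Suppose a fraction c of d is still present in the Day 2 pre-infusion reading after Flebogamma on Day 1. Then the Day 2 change is (1 − c) × d at 2 g/kg. In the 1 g/kg arm it is −c × d for Flebogamma-first subjects (now on saline) and d for saline-first subjects. At pi = 0.5 the 1 g/kg Day 2 mean is 0.5 × (1 − c) × d, half the 2 g/kg value:

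- c = 0.25, d = 5: 1.88 against 3.75.
- c = 0.50, d = 5: 1.25 against 2.50.

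The within-subject Flebogamma-minus-saline difference then depends on order. It is d − (−c × d) = (1 + c) × d for Flebogamma-first subjects and d for saline-first subjects. For c = 0.25 and d = 5 that is 6.25 against 5.00, so it should not be pooled over order without looking.

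**The case against.** The strongest reply is that arms are regimens. The 1 g/kg regimen is one Flebogamma and one saline infusion per cycle, and a smaller average per arm-day describes it correctly. This stands. A reader might infer that the table shows a false dose gradient outright; the documents do not support that, because the SAP nowhere offers the table as a per-infusion dose response. The gradient is misleading only under that reading.

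A reader might also infer that the effect is halved on each day. That needs a 1:1 order, which no passage states. Without carry-over, only the two-day average is exactly half.

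Nor can the endpoint be read as meaning change during Flebogamma infusions alone. Protocol 9.2.2 covers infusions of either product and handles clinically relevant changes as adverse events on the investigator's judgement.

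The size is also unknown. The documents give no acute vital-sign effect, and two of the three post-start readings come early. Under the initial rates in Protocol 4.4.4.3, 0.01 × 30 = 0.3 mL/kg has been infused at 30 minutes and 0.3 + 0.02 × 30 = 0.9 mL/kg at 60 minutes. These are 1.5% and 4.5% of the day's 20 mL/kg. If d is near zero at those times, the dilution there is negligible.

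The remaining defences do not repair the table. Listing all vital signs leaves the summary as it is. Analysis by actual treatment received does not help, since a correctly treated 1 g/kg subject contributes one day of each product. The infusional adverse events in SAP 11.1 use the whole two-day period plus 72 hours, so they do not separate the products either.

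**Conclusion.** The point holds as a presentation problem in a descriptive safety table. In the 1 g/kg arm each by-day cell mixes two products. Its contrast with placebo is pi × d and (1 − pi) × d, averaging 0.5d, against d on each day at 2 g/kg. This assumes no carry-over and a common per-infusion effect d in both active arms, with d and pi unknown. Read per infusion, the table understates the acute Flebogamma effect at 1 g/kg and can suggest a gradient between doses. Read as a summary of the two-day regimen, it is not wrong.

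A reader might go further and infer that dose selection or the efficacy conclusion is compromised. The documents do not support this. The selection rule in SAP 5.4 uses conditional power on 2MWD. It presupposes no safety concern, but does not tie that judgement to this table. The primary analysis does not use vital signs. The data can be re-tabulated without loss, so this is a cheap improvement.

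**What to change.** In SAP 11.3, use the IWRS order to tabulate the 1 g/kg arm by product within each day: Day 1 Flebogamma, Day 1 saline, Day 2 Flebogamma, Day 2 saline. Set these beside Day 1 and Day 2 of the 2 g/kg and placebo arms, so that each 1 g/kg cell is compared with the same day elsewhere. Pooling all Flebogamma days into one column would not do this, because it mixes Day 1 and Day 2. If a within-subject Flebogamma-minus-saline difference is added, show it separately by order because of possible carry-over. The by-day regimen summary can stay, with a footnote saying that its 1 g/kg cells contain both products.

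The cost is one derived variable (product by day) merged after unblinding, and smaller cells. In 42 subjects there would be 42/2 = 21 per cell if the order is 1:1. With pi between 0.35 and 0.65, cells would run from about 15 (42 × 0.35 = 14.7) to about 27 (42 × 0.65 = 27.3). No new data and no change to trial conduct are needed.

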11.4 Physical Assessments

Abnormal physical assessment findings at screening will be summarized using counts and percentages of subjects, by body system. Entries for 'Other' body systems will be grouped together; a subject with 2 or more 'Other' entries will be counted only once. Counts and percentages of subjects with new or worsening findings post-screening will be presented by treatment group.

All physical assessment data will be listed.

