4.5.2.2 Physical assessment

A physical examination by body systems will be performed by a medical doctor at the SV (Week -4 to -1), IV7 (Week 24), EoTV (Week 52), and FV (Week 76).

The physical examination performed at the SV will include identification of the main body part (i.e., lower extremities versus upper extremities) that is most significantly affected by PPS for the purpose of stratifying randomization. Identification of the body part most significantly affected by PPS may also take into consideration findings obtained by neurological examination at the SV (Section 4.5.2.3). Selection of stratification must be documented in the medical notes.

Alternatively, the physical assessment will be carried out at the EV/IV1 (Week 0), IV4 (Week 12), IV10 (Week 36) and Follow-Up Visit 3 (FU3; Week 64).

Subject's height and weight will be measured at the SV (Week -4 to -1) in order to calculate his/her body mass index (BMI). At the EV/IV1 (Week 0), IV4 (Week 12), IV7 (Week 24) and IV10 (Week 36) the subject's weight will be measured again.

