5.2 Treatment period

Those individuals who have been enrolled will attend to their investigational site for intravenous infusions every 4 weeks, counted from the date of randomization. Different study

and safety of Immune Globulin Intravenous (Human) Flebogamma® 5% DIF in patients with Post-Polio Syndrome

assessments will be performed according to the infusion visit number. A \pm 1-week window is allowed for all study visits in the treatment period after the EV/IV1.

Sites affected by the COVID-19 pandemic can refer to ANNEX 18 for extraordinary contingency measures to be implemented.

Enrollment Visit (EV)/Infusion Visit 1 (IV1)

This visit will include 2 visits: Enrollment Visit (EV) and Infusion Visit 1 (IVI 1). Assessments and procedures for the EV will take place prior to the planned first infusion (IV1) to assess patient's consistency regarding the 2MWD, to confirm the patient's eligibility for the study, and to obtain baseline values/assessments.

Assessments and procedures planned to be done during the EV will be performed over different days within a 1-week time window:

ENROLLMENT VISIT:

- 1. Physical assessment.
- 2. Weight.
- Concomitant medication.
- 4. AEs.

*Procedures 5 through 10 must be performed in the following order on the same day:

- Subject questionnaires: Fatigue (Baseline FSS); HRQoL (Baseline SF-36); Pain (Baseline VAS for pain).
- 6. Record/upload number of steps from pedometer during 7 consecutive days prior to visit: Baseline Walking Activity in daily life.
- 7. Physical performance: Baseline 2MWD with assessment of perceived exertion/fatigue by Borg scale immediately before and immediately after 2MWD; this 2MWD will be used to assess inclusion criteria 10 and to calculate 2MWD consistency between SV and EV assessments (inclusion criterion 11).
- 8. Rest period (sitting on a chair for at least 30 minutes and until the subject feels fully recovered after completion of the 2MWD).
- 9. Endurance: Baseline 6MWD with assessment of perceived exertion/fatigue by Borg scale immediately before and immediately after 6MWD.
- 10. Review of the clinical trial inclusion criteria 10 and 11 and all exclusion criteria to confirm subject eligibility.
- *Procedures 11 through 13 must be performed on the 2 muscle groups selected at the SV.
- *Procedures 11 through 15 must be performed prior to IV1 in the following order on the same day and on different day than earlier assessments:
- 11. Muscle strength: Baseline MMT.

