- 12. Rest period (sitting on a chair for at least 30 minutes and until the subject feels fully recovered after completion of the MMT).
- 13. Muscle strength: Baseline QMT.

14. Randomization.

Individuals who fulfill all inclusion criteria and none of the exclusion criteria and have undergone all screening and enrollment assessments will be considered eligible to continue in the clinical trial. These subjects will be randomized to 1 of the treatment arms and will be included in the *IWRS Randomization*. Randomization is to be stratified based on the body part (lower extremities versus upper extremities) that was most significantly affected by PPS at the SV.

Individuals who do not fulfill all of the inclusion criteria, fulfill any of the exclusion criteria, or have not undergone all enrollment assessments will be considered enrollment failures. If a subject is ineligible for the clinical trial, their demographic data and specific reason for ineligibility will be captured on the appropriate eCRF page and on the medical history eCRF.

INFUSION VISIT 1:

Investigational product will be infused at IV1 over 2 consecutive days (Day 1 and Day 2) which will start on the same day or after finishing the Enrollment Visit.

Infusion Day 1:

- 1. Blood testing (blood sample collected within 8 hours prior to the infusion):
 - Blood biochemistry and cell counts: CBC, including differential leukocyte count, creatinine, BUN, ALT, AST, ALP, TBL, and GFR.
 - D-dimer blood level for thromboembolic events risk assessment.
 - Hemolysis detection: whole blood hemoglobin, serum or plasma free hemoglobin, haptoglobin, LDH, DAT, ARC, RBC, hematocrit, total and indirect bilirubin, and blood smear.
 - Inflammatory cytokines: IL-1, IL-4, IL-6, IL-10, IL-13, IL-17, IL-23, TNF-alpha, and IFN-gamma.
 - Retention blood sample for possible viral exposure testing (sample will be tested only if subject shows signs and symptoms of viral infection during the study).
 - Retention blood sample for possible future biomarker testing.
- 2. Urine testing (urine sample collected within 8 hours prior to the infusion):
 - Urine sediment and measuring of hemoglobinuria.
- 3. Infusion and vital signs:
 - Infusion of investigational product.
 - Subject vital signs (T, RR, HR, SBP and DBP) will be monitored: (1) within 20 minutes before the beginning of each infusion; (2) every 30 ± 10 minutes during the first hour of each infusion; and (3) at 30 ± 10 minutes post-completion of each infusion.

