AEs temporally associated to the infusion of the investigational products (*i.e.*, infusional AEs, including infusional suspected ADRs), will be summarized by presenting infusion/subject incidences and percentage and ordered by ordinal number of infusions, and listed. In addition, the infusion rate in effect at the time of onset of the AE, the time the AE is first reported, and the time the AE changes materially in intensity and/or resolves will be also reported and listed. In addition, AEs temporally associated to the infusion of the investigational products for which the incidence in the Flebogamma[®] 5% DIF exceeds the incidence in the placebo group will be summarized separately.

Subjects with a serious adverse event (SAE) or who withdraw from the study because of an AE will also be individually listed and summarized.

AEs for which the investigator causality assessment is missing or undetermined will be individually listed.

Vital signs during infusions:

Vital signs (T, RR, HR, SBP and DBP) will be listed for each clinical trial subject. In case a subject presents a clinically relevant abnormality of vital signs (based on the Investigator's judgment) during an infusion, the event will be flagged and reported as an AE temporally associated to the infusion. All vital signs will be evaluated for each subject and for each infusion.

Physical assessment:

Physical findings (normal and abnormal) will be listed for each clinical trial subject. Any clinically relevant abnormality (based on the Investigator's judgment) developed by individual during the clinical trial and not already present at baseline will be reported as AE.

Blood biochemistry and cell counts:

All clinical laboratory data for renal (creatinine, BUN and GFR), hepatic (ALT, AST, ALP and TBL) and haematological parameters (CBC including differential leukocyte count) will be listed for each clinical trial subjects. Laboratory results out of the normal range judged by the Investigator as clinically relevant will be considered AEs.

	Number	GLB-PRT-FLB-IG1104	Version	7.0	Status	Effective	Effective Date	07-Mar-2022
CIVILOLS	IG1104 - A n	multicenter, prospective, randomized, placebo-controlled,	, double-blind	l, parallel-gro	up clinical trial	to assess the efficacy		70 F 3 - 00 F
Bioscience Industrial Group	and safety or	of Immune Globulin Intravenous (Human) Flebogamma®	5% DIF in pa	tients with P	ost-Polio Syndı	ome	rage	108 01 122

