5.1 Data Handling

Unless otherwise noted, if an observation is missing at a specific scheduled visit/timepoint, the value at that visit will not be imputed and will be set to missing in summary tables.

Baseline will be defined as the measurement taken at the Enrollment Visit (EV)/Infusion Visit 1 (IV1) or the last measurement taken prior to the start of the study treatment if the parameter is not measured at the Enrollment Visit (EV)/Infusion Visit 1 (IV1) or there are multiple observations for the parameter at the Enrollment Visit (EV)/Infusion Visit 1 (IV1).

For table summaries, the data will be presented at the scheduled visits according to protocol. For early terminated subjects, the termination visit occurred at End of Study will be remapped to the subject's next scheduled visit for analysis and summary. Any data collected at the unscheduled visits will be listed in data listings.

5.1.1 **VAS Correction**

For cases where VAS was recorded on the scale sizes of X(mm) other than 100mm, the VAS score will be recalculated as

$$VAS_{=}VAS_{recorded} * \frac{100}{X}$$

The tracker file "IG1104 VAS scale issue 100 mm.xlsx" includes all the protocol deviations of VAS records with scales other than 100mm. The adjusted VAS score will be implemented for the cases included in the tracker file. The unadjusted and adjusted VAS scores will be presented in the relevant CSR listing with a flag to indicate which VAS scores were adjusted. A footnote will be included to explain the rescaling of the VAS scores.

5.2 **Analysis Populations**

In this study, three analysis populations are defined as:

Intent to treat (ITT) population

The Intent-to-treat (ITT) population consists of all subjects randomized.

Per-protocol (PP) population

The Per-protocol (PP) population consists of all subjects in the ITT population who have received at least 8 infusions, without having 2 consecutive missed infusions of any investigational product (test or placebo) during the treatment period, have baseline and at least one post-baseline measures of the 2MWD, and have no critical or major protocol deviations that might have impact on the primary efficacy assessment (as determined at a data review meeting prior to database lock and unblinding).

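### SAP 11.4 counts new or worsening physical findings from screening onward, so findings recorded at Week 0 before any infusion are tabulated under a treatment arm (low impact)

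*SAP*

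**What the plan says.** SAP 11.4 plans two summaries of physical findings. The first is of pre-existing abnormalities: "Abnormal physical assessment findings at screening will be summarized using counts and percentages of subjects, by body system". The second is the comparison by arm: "Counts and percentages of subjects with new or worsening findings post-screening will be presented by treatment group". All physical assessment data are also listed. The section sets no condition that a finding must start after the first infusion, and it does not exclude Week 0.

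Protocol 4.5.2.2 and Table 6 schedule two kinds of check. The examination by body systems is at the Screening Visit (SV), IV7, EoTV and FV. A less closely specified physical assessment is at EV/IV1, IV4, IV10 and FU3. Table 6 shows both in one row, and only the SV lies in its screening period.

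On timing, Protocol 5.2 states: "Assessments and procedures for the EV will take place prior to the planned first infusion (IV1"). The physical assessment is the first listed EV procedure and randomization is the fourteenth. The infusion is one "which will start on the same day or after finishing the Enrollment Visit".

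SAP 5.1 sets the general reference: "Baseline will be defined as the measurement taken at the Enrollment Visit (EV)/Infusion Visit 1 (IV1"), or the last measurement before treatment if the parameter is not measured at that visit or is measured there more than once.

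**The concern.** A count of new or worsening findings by arm is useful for safety only if it describes what happened after exposure. A finding that first appears at Week 0 precedes both allocation and drug, so it carries no information about either, yet the rule as worded places it in the column of the arm the subject then joins. The same happens to a finding that arises after the SV and is still present at Week 12 or later: measured against screening it is new, although it predates treatment.

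The result is a background of pre-dose findings in every arm of a table on a named safety variable (SAP 4.2). The table also follows a different convention from the other safety summaries in the same chapter, so a reader of the study report could not line it up with them.

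**Working it through.** The plan gives no figure for this table, so there is none to reproduce. The check sets the passages side by side.

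**Step 1: is Week 0 inside the window?** Table 6 places only the SV in the screening period and makes EV/IV1 the first treatment-period column, with the physical assessment marked. So Week 0 is post-screening whether that means after the visit or after the period. SAP 11.4 is titled for physical assessments generally, and Table 6 has one row for both kinds of check, so the Week 0 assessment is in scope.

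**Step 2: is it before treatment?** Yes. It is the first EV item, randomization is item 14, and the infusion waits for the EV to be finished. Table 6, footnote a, asks for procedures to follow the order in Section 5.

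**Step 3: count the visits.**
- Scheduled post-screening assessments: Weeks 0, 12, 24, 36, 52, 64 and 76, which is 7.
- Of these, after the first infusion: Weeks 12, 24, 36, 52, 64 and 76, which is 6.
- Pre-dose: 7 − 6 = 1.

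**Step 4: would dropping the Week 0 records be enough?** No. The SV falls in Week −4 to −1, so a finding can arise in an interval of up to about 4 weeks before Week 0. If it persists, it is still new against screening at Week 12. The reference status has to change as well as the window.

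**Step 5: compare with the rest of the plan.**

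| Place | Reference or rule |
|---|---|
| SAP 5.1 | EV/IV1, or the last pre-treatment measurement |
| SAP 11.1 | adverse events before treatment kept apart as non-TEAEs |
| SAP 11.2 | laboratory change from baseline |
| SAP 11.3 | vital-sign change from the pre-infusion reading |
| SAP 11.4 | new or worsening since screening |

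SAP 11.4 is the only one that measures change from screening. SAP section 12, on changes to protocol-specified analyses, gives no reason for this.

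**Step 6: size.** The documents give no rate of findings first seen between the SV and EV/IV1, so the inflation cannot be quantified. Purely as an illustration, assume independent post-infusion risks of p = 10% (placebo) and 20% (active), and a proportion e with a pre-dose finding. The table would show 1 − (1 − e)(1 − p) in each arm. The difference is (1 − e) × 10 points.

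| e (assumed) | Placebo | Active | Difference | Ratio |
|---|---|---|---|---|
| 0 | 10.0% | 20.0% | 10.0 points | 2.00 |
| 0.55% | 10.5% | 20.4% | 9.9 points | 1.95 |
| 2% | 11.8% | 21.6% | 9.8 points | 1.83 |
| 5% | 14.5% | 24.0% | 9.5 points | 1.66 |
| 10% | 19.0% | 28.0% | 9.0 points | 1.47 |

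The 0.55% row spreads the assumed placebo risk evenly over 76 weeks and takes 4 of them: 1 − 0.90^(4/76) = 0.0055. All these rates are assumptions.

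**The case against.** The strongest defence is that screening is a reasonable reference. The examination by body systems is not repeated until IV7, and SAP 5.1 itself falls back on the last pre-treatment measurement where a parameter is not measured at EV/IV1. For a body system not looked at in Week 0, that is the SV. This stands, and the fix has to respect it. It does not justify counting a finding that was recorded before the first infusion.

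There are four stronger readings that the documents do not support.

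- **That the comparison between arms is biased.** The Week 0 assessment precedes randomization, so no systematic imbalance is expected. The effect is added background in every arm.
- **That this is the only comparison of physical findings by arm.** Findings judged clinically relevant are adverse events (Protocol 9.2.3), and SAP 11.1 tabulates those by treatment group with onset handled correctly. What lacks a second route is the finding not judged clinically relevant.
- **That SAP 11.4 breaks a protocol-specified analysis.** Protocol 10.1.3 says an abnormality "developed by individual during the clinical trial and not already present at baseline will be reported as AE", but that sentence governs adverse-event reporting. For physical findings as such, the section plans a listing only. Nor does SAP 11.4 label its count treatment-emergent.
- **That the active-to-placebo ratio is materially diluted.** This depends wholly on the assumed pre-dose rate. In the illustration the risk difference moves only from 10.0 to 9.5 points at e = 5%, and with the evenly spread rate the ratio stays at 1.95.

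**Conclusion.** The point holds as a low-impact defect in the definition of one safety table. As worded, SAP 11.4 attributes to an arm findings that predate randomization and the first infusion, and it departs from the conventions in SAP 5.1 and 11.1. It inflates the counts in every arm by an amount the documents do not allow to be estimated. The only size they support is that 1 of 7 scheduled post-screening assessments is pre-dose.

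The conclusion rests on reading post-screening literally and on Week 0 assessments being recorded with the other physical assessment data, as Table 6 suggests. The table is descriptive, with no test or decision attached, and the listings would let a reader identify Week 0 findings. The reason to act is that the correction is cheap and makes the table interpretable, not that any conclusion of the trial is at risk.

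**What to change.** In SAP 11.4, replace the post-screening rule with the following:

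- Count by treatment group only findings first recorded, or worsened, after the start of the first infusion, compared with the last pre-infusion status of that body system.
- Take that status from the SV examination and carry it forward unless EV/IV1 explicitly records a change. A system not reassessed at EV/IV1 keeps its SV status, so silence at Week 0 is not read as resolution.
- Show findings first recorded at EV/IV1 separately, as pre-treatment.

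The cost is a short text change, one extra derivation of pre-infusion status with a date condition in the program, and slightly lower counts in the table. No new data are needed.
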